**Cockcroft-Gault Equation:**

$$\text{Creatinine clearance for males} = \frac{(140 - \text{age})(\text{weight in kg})}{(72)(\text{serum creatinine in mg/dL})}$$

$$\text{Creatinine clearance for females} = \frac{(140 - \text{age})(\text{weight in kg})(0.85)}{(72)(\text{serum creatinine in mg/dL})}$$

- International Normalized Ratio (INR) or Prothrombin Time (PT) and activated Partial Thromboplastin Time (aPTT)  $\leq 1.5 \times$  ULN unless patient is receiving anticoagulant therapy as long as PT or PTT is within therapeutic range of intended use of anticoagulants

3.19a Adequate cardiac function:

- Left ventricular ejection fraction (LVEF)  $\geq 50\%$  as determined by multigated acquisition (MUGA) scan or echocardiogram (echo)
- QTc interval  $\leq 480$  ms

3.19b Negative serum pregnancy test done  $\leq 7$  days prior to registration, for women of childbearing potential only.

3.19c Able to swallow oral medication.

3.19d Both female and male patients of reproductive potential must agree to avoid pregnancy or impregnating a partner (respectively) while receiving drug and for 120 days after last dose of study drug. (See Section 9.0 for specific requirements).

3.19e Provide written informed consent.

3.19f Willing to return to enrolling institution for follow-up (during the Active Monitoring Phase of the study).

3.19g Willing to provide mandatory tissue and blood for correlative research purposes (see Sections 6, 14 and 17).

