**Cockcroft-Gault Equation:**

$$\text{Creatinine clearance for males} = \frac{(140 - \text{age})(\text{weight in kg})}{(72)(\text{serum creatinine in mg/dL})}$$

$$\text{Creatinine clearance for females} = \frac{(140 - \text{age})(\text{weight in kg})(0.85)}{(72)(\text{serum creatinine in mg/dL})}$$

International Normalized Ratio (INR) or Prothrombin Time (PT) and activated Partial Thromboplastin Time (aPTT)  $\leq 1.5 \times$  ULN unless patient is receiving anticoagulant therapy as long as PT or PTT is within therapeutic range of intended use of anticoagulants

3.35 Females of childbearing potential should have a negative serum or urine pregnancy test  $\leq 72$  hours prior to re-registration.

3.36 Females or males of childbearing potential must be willing to use adequate methods of contraception as outlined in section 9.9b or abstain from heterosexual activity for the course of the study through 120 days after last dose of study medication.

3.37 Experienced an investigator-determined confirmed radiographic disease progression after stopping their initial treatment with pembrolizumab and binimatinib.

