## 7.5 Retreatment (Second Course Phase)

Patients who stop pembrolizumab and binimetinib with SD or better may be eligible for up to one year of additional pembrolizumab and binimetinib therapy if they progress after

stopping study treatment. This retreatment is termed the Second Course Phase of this study and is only available if the study remains open and the patient meets the following conditions:

EITHER

- Stopped initial treatment with pembrolizumab and binimatinib after attaining an investigator-determined confirmed CR according to RECIST 1.1, and
  - Was treated for at least 24 weeks with pembrolizumab and binimatinib before discontinuing therapy
  - Received at least two cycles with pembrolizumab and binimatinib beyond the date when the initial CR was declared

OR

- Had SD, PR or CR and stopped pembrolizumab and binimatinib treatment after 24 months of study therapy for reasons other than disease progression or intolerance

AND

- Experienced an investigator-determined confirmed radiographic disease progression after stopping their initial treatment with pembrolizumab and binimatinib
- Did not receive any anti-cancer treatment since the last dose of pembrolizumab and binimatinib
- Has a performance status of 0 or 1 on the ECOG Performance Scale
- Demonstrates adequate organ function (as required for initial eligibility in Section 3.0)
- Females of childbearing potential should have a negative serum or urine pregnancy test within 72 hours prior to receiving retreatment with study medication
- Females or males of childbearing potential must be willing to use adequate methods of contraception as outlined in [Section 9.9b](#) or abstain from heterosexual activity for the course of the study through 120 days after the last dose of study medication.
- Does not have a history or current evidence of any condition, therapy, or laboratory abnormality that might interfere with the subject's participation for the full duration of the trial or is not in the best interest of the subject to participate, in the opinion of the treating investigator.

Baseline procedures as outlined in the pretrial screening should be repeated  $\leq 28$  days prior to retreatment.

Patients who restart treatment will be retreated at the same dose and dose interval as when they last received pembrolizumab and binimatinib. Patients may continue treatment for up to one additional year and will follow the original treatment schedule starting at cycle 2.

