#### 9.9b Contraception

Pembrolizumab may have adverse effects on a fetus in utero. Furthermore, it is not known if pembrolizumab has transient adverse effects on the composition of sperm.

For this trial, male patients will be considered to be of non-reproductive potential if they have azoospermia (whether due to having had a vasectomy or due to an underlying medical condition).

Female patients will be considered of non-reproductive potential if they are either:

(1) postmenopausal (defined as at least 12 months with no menses without an alternative medical cause; in women <45 years of age a high follicle stimulating hormone (FSH) level in the postmenopausal range may be used to confirm a post-menopausal state in women not using hormonal contraception or hormonal replacement therapy. In the absence of 12 months of amenorrhea, a single FSH measurement is insufficient.);

OR

(2) have had a hysterectomy and/or bilateral oophorectomy, bilateral salpingectomy or bilateral tubal ligation/occlusion, at least 6 weeks prior to screening;

OR

(3) has a congenital or acquired condition that prevents childbearing.

Female and male patients of reproductive potential must agree to avoid becoming pregnant or impregnating a partner, respectively, while receiving study drug and for 120 days after the last dose of study drug by complying with one of the following:

(1) practice abstinence† from heterosexual activity;

OR

(2) use (or have their partner use) acceptable contraception during heterosexual activity.

Acceptable methods of contraception are‡:

Single method (one of the following is acceptable):

- intrauterine device (IUD)
- vasectomy of a female subject's male partner
- contraceptive rod implanted into the skin

Combination method (requires use of two of the following):

- diaphragm with spermicide (cannot be used in conjunction with cervical cap/spermicide)
- cervical cap with spermicide (nulliparous women only)
- contraceptive sponge (nulliparous women only)
- male condom or female condom (cannot be used together)
- hormonal contraceptive: oral contraceptive pill (estrogen/progestin pill or progestin-only pill), contraceptive skin patch, vaginal contraceptive ring, or subcutaneous contraceptive injection

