†Abstinence (relative to heterosexual activity) can be used as the sole method of contraception if it is consistently employed as the subject's preferred and usual lifestyle and if considered acceptable by local regulatory agencies and ERCs/IRBs. Periodic abstinence (e.g., calendar, ovulation, sympto-thermal, post-ovulation methods, etc.) and withdrawal are not acceptable methods of contraception.

‡If a contraceptive method listed above is restricted by local regulations/guidelines, then it does not qualify as an acceptable method of contraception for patients participating at sites in this country/region.

Patients should be informed that taking the study medication may involve unknown risks to the fetus (unborn baby) if pregnancy were to occur during the study. In order to participate in the study patients of childbearing potential must adhere to the contraception requirement (described above) from the day of study medication initiation (or 14 days prior to the initiation of study medication for oral contraception) throughout the study period up to 120 days after the last dose of trial therapy. If there is any question that a patient of childbearing potential will not reliably comply with the requirements for contraception, that patient should not be entered into the study.

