#### **10.821    Pregnancies**

To ensure patient safety, each pregnancy occurring while the patient is on study treatment must be reported to Pfizer within 24 hours of learning of its occurrence. The pregnancy should be followed up to determine outcome, including spontaneous or voluntary termination, details of the birth, and the presence or absence of any birth defects, congenital abnormalities, or maternal and/or newborn complications.

Pregnancy should be recorded on a Clinical Trial Pregnancy Form and reported by the investigator to Pfizer Drug Safety. Pregnancy follow-up should be recorded on the same form and should include an assessment of the possible relationship to the study treatment any pregnancy outcome. Any SAE experienced during pregnancy must be reported on the SAE Report Form.

Pregnancy outcomes must be collected for the female partners of any males who took study treatment in this study. Consent to report information regarding these pregnancy outcomes should be obtained from the mother.

Women of childbearing potential should be advised to use highly effective contraception methods while they are receiving study treatment and up to 8 weeks after treatment has been stopped.

If a pregnancy occurs while on study treatment, the newborn will be followed for at least 3 months following the expected delivery date

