**15.25 Pharmacokinetic information:**

- a) Absorption – Because pembrolizumab is administered intravenously, it is immediately and completely bioavailable. Steady-state concentrations of pembrolizumab are reached by 16 weeks of repeated dosing with a Q3W regimen and the systemic accumulation is 2.1-fold. The peak concentration, trough concentration, and area under the plasma concentration versus time curve at steady state of pembrolizumab increased dose proportionally in the dose range of 2 to 10 mg/kg Q3W.
- b) Distribution – Pembrolizumab has a limited volume of distribution.
- c) Excretion – CL is approximately 23% lower after achieving maximal change at steady state compared with the first dose. The terminal elimination half-life( $t_{1/2}$ ) is estimated to be 22 days at steady state.
- d) Metabolism – Pembrolizumab is catabolized through non-specific pathways; metabolism does not contribute to its CL.

15.26 **Potential Drug Interactions:** There are no known significant drug interactions.

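### Section 10.821 advises women to use contraception for 8 weeks after treatment, against the binding 120 days in Sections 3.19d, 3.36, 7.5 and 9.9b

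*Combined protocol and SAP*

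**What the plan says.** The protocol states a contraception period in five places.

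- **Section 10.821 (Pregnancies)**, under the instructions for reporting to Pfizer, says that women of childbearing potential should be advised to use highly effective contraception "while they are receiving study treatment and up to 8 weeks after treatment has been stopped".
- **Section 3.19d (inclusion criterion)** makes both sexes agree to avoid pregnancy "while receiving drug and for 120 days after last dose of study drug".
- **Section 9.9b (Contraception)** sets the main rule, "while receiving study drug and for 120 days after the last dose of study drug". Its closing paragraph repeats it as a condition of taking part, "throughout the study period up to 120 days after the last dose of trial therapy".
- **Section 3.36 (retreatment inclusion criterion)** requires willingness to use contraception or abstain "through 120 days after last dose of study medication", and points to Section 9.9b for the methods.
- **Section 7.5 (Second Course Phase)** repeats that condition, "through 120 days after the last dose of study medication", and also points to Section 9.9b.

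Section 9.9b opens by warning that pembrolizumab may harm a fetus. Section 15.25 gives its terminal half-life, which "is estimated to be 22 days at steady state".

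**The concern.** One protocol gives two different periods for the same precaution, and the shorter one is a direct instruction on what to tell patients. It sits under a heading where site staff would plausibly look when a question about pregnancy comes up. Agreement to 120 days is obtained at entry, whereas advice on the post-treatment period may well be given again when treatment ends, and that could be as much as two years later.

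A woman counselled from Section 10.821 at that point would be told she could stop contraception well before Section 9.9b allows, while pembrolizumab is still being cleared. The conflict concerns women only, because the sentence in Section 10.821 does not address contraception by men.

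**Working it through.** No design figure of the plan is involved, so the check is a comparison of texts followed by simple arithmetic.

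**1. Which rule binds**

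| Section | Applies to | Force | Period after stopping |
|---|---|---|---|
| 3.19d | All patients, both sexes | Mandatory (eligibility) | 120 days |
| 9.9b (two statements) | All patients, both sexes | Mandatory | 120 days |
| 3.36 | Retreatment, both sexes | Mandatory (eligibility) | 120 days |
| 7.5 | Retreatment, both sexes | Mandatory | 120 days |
| 10.821 | Women of childbearing potential | Advisory | 8 weeks |

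Four sections agree, all four are mandatory, and the two retreatment sections cite Section 9.9b. The 120 days is therefore the rule, and Section 10.821 is the outlier.

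**2. Whether the 8 weeks is limited to binimetinib**

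The sentence refers to study treatment without qualification. Section 10.82 elsewhere allows for more than one study treatment, and it adds the company's name when it means only that company's drug. So the text of Section 10.821 does not confine the 8 weeks to binimetinib. Even if it did, Section 9.9b sets 120 days after study drug and trial therapy and makes no exception for binimetinib.

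**3. Size of the gap, counted from a common stop date**

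- 8 weeks × 7 = 56 days
- 120 − 56 = 64 days short
- 56 / 120 = 0.467, so the advice covers 47% of the required period

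**4. Pembrolizumab remaining at the end of each period**

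Input: half-life of 22 days (Section 15.25). Formula: fraction remaining = 0.5^(t/22), with t in days since the last pembrolizumab dose. This assumes simple exponential decline.

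| Situation | t (days) | Half-lives, t/22 | Fraction remaining |
|---|---|---|---|
| 8 weeks, starting at the last pembrolizumab dose | 56 | 2.55 | 0.171, about 17% |
| 8 weeks, starting when binimetinib ends at about day 21 of the last cycle | 21 + 56 = 77 | 3.5 | 0.088, about 9% |
| 120 days after the last pembrolizumab dose | 120 | 5.45 | 0.023, about 2% |

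The second row is needed because Section 7.1 gives pembrolizumab on day 1 of each cycle and binimetinib on days 1 to 21. When treatment stops therefore depends on which drug ends last. Section 8.1 lets a patient who has discontinued binimetinib continue on pembrolizumab alone, and for her the first row applies.

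**The case against.** The strongest reply is that the risk is already controlled. A woman cannot be registered without agreeing to 120 days (Section 3.19d). Section 3.21 excludes anyone unwilling to use contraception as Section 9.0 defines it, and Section 9.9b says that a patient whose compliance is in doubt should not be entered. Section 10.821 is only advisory, and a woman who follows the 120-day rule also satisfies the 8-week advice. All of this stands. It is why the shortfall is potential rather than built in, but it does not make the shorter advice right.

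A second reply is that the 8 weeks probably comes from text specific to binimetinib, since it sits in the Pfizer section and Pfizer supplies only that drug. That is plausible, but it is an inference that the sentence does not state, and the reader is not told which period governs.

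A third reply is that 17% is not a fixed figure. This is correct: it applies when the 8 weeks starts at the last pembrolizumab dose, and falls to about 9% if binimetinib runs to the end of the last cycle. The documents also give no concentration below which fetal risk is negligible, so neither percentage measures harm. The 64-day difference depends on neither point, provided both periods are counted from the same date.

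Finally, it may be said that Section 9.9b does not itself contain the words proposed below about either drug and the later date. They are a fair reading of its reference to the last dose of trial therapy, and they settle the case in which the two drugs stop at different times.

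**Conclusion.** The concern holds. Section 10.821 gives a contraception period of 56 days where the binding rule is 120 days, a gap of 64 days, and nothing in the section limits or subordinates the shorter figure. The sentence is wrong as written and should be corrected.

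The consequence depends on a site counselling from Section 10.821 instead of Section 9.9b. The pharmacokinetic figures (about 17%, or about 9% if binimetinib is the last drug stopped, against about 2%) rest on the stated 22-day half-life and simple exponential decline, and are only illustrative. This is an inconsistency in a safety instruction for women; no endpoint, sample size, analysis or decision rule is affected.

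**What to change.** In Section 10.821, replace the 8-week period with: *for 120 days after the last dose of either study drug, whichever is later, as required in Section 9.9b*. If the sponsor means the 8 weeks for binimetinib alone, the section should say so and state that the longer period governs.

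The cost is one sentence. No other section has to change, and eligibility, visit schedule, sample size and analysis stay as they are. While editing it, the sponsor could also take the methods of contraception by reference from Section 9.9b, because Section 10.821 asks for highly effective methods and Section 9.9b lists acceptable ones.

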#### **10.822    Warnings and precautions**

No evidence available at the time of the approval of this study protocol indicated that special warnings or precautions were appropriate, other than those noted in the provided Investigator Brochure. Additional safety information collected between IB updates will be communicated in the form of Investigator Notifications. This information will be included in the patient informed consent and should be discussed with the patient during the study as needed.

## 11.0 Treatment Evaluation

Response and progression will be evaluated in this study using the new international criteria proposed by the revised Response Evaluation Criteria in Solid Tumors (RECIST) guidelines (version 1.1) and by the ESMO 2014 Adaptation of the Immune-Related Response Criteria: irRECIST {Bohnsack 2014}. RECIST version 1.1 will be used for assessment of tumor response for the primary endpoint. **irRECIST will be used to make patient management decisions during the trial.**

Changes in the largest diameter (unidimensional measurement) of the tumor lesions and the short axis measurements in the case of lymph nodes are used in the RECIST 1.1 and irRECIST guidelines. **In RECIST 1.1, the appearance of new lesions automatically signifies progressive disease (PD), while in irRECIST new measurable lesions are factored into the total tumor burden.** The specifics are presented below.

NOTE: This study uses protocol RECIST v1.1 template dated 2/16/2011. See the footnote for the table regarding measurable disease in Section 11.44, as it pertains to data collection and analysis.

### 11.1 Schedule of Evaluations

For the purposes of this study, patients should be reevaluated every 6 weeks. In addition to a baseline scan, confirmatory scans should also be obtained 4 weeks following initial documentation of objective response.

### 11.2 Definitions of Measurable and Non-Measurable Disease (same definitions for RECIST 1.1 and irRECIST)

#### 11.21 Measurable Disease

11.211 A non-nodal lesion is considered measurable if its longest diameter can be accurately measured as  $\geq 2.0$  cm with chest x-ray, or as  $\geq 1.0$  cm with CT scan, , or MRI.

11.212 A superficial non-nodal lesion is measurable if its longest diameter is  $\geq 1.0$  cm in diameter as assessed using calipers (e.g. skin nodules) or imaging. In the case of skin lesions, documentation by color photography, including a ruler to estimate the size of the lesion, is recommended.

11.213 A malignant lymph node is considered measurable if its short axis is  $>1.5$  cm when assessed by CT scan (CT scan slice thickness recommended to be no greater than 5 mm).

**NOTE:** Tumor lesions in a previously irradiated area are not considered measurable disease.

#### 11.22 Non-Measurable Disease

11.221 All other lesions (or sites of disease) are considered non-measurable disease, including pathological nodes (those with a short axis  $\geq 1.0$  to  $<1.5$  cm). Bone lesions, leptomeningeal disease, ascites, pleural/ pericardial effusions, lymphangitis cutis/pulmonis, inflammatory breast disease, and abdominal masses (not followed by CT or MRI), are considered as non-measurable as well.

Note: 'Cystic lesions' thought to represent cystic metastases can be considered as measurable lesions, if they meet the definition of measurability described above. However, if non-cystic lesions are present in the same patient, these are preferred

for selection as target lesions. In addition, lymph nodes that have a short axis  $<1.0$  cm are considered non-pathological (i.e., normal) and should not be recorded or followed.

### **11.3 Guidelines for Evaluation of Measurable Disease**

#### **11.31 Measurement Methods:**

- All measurements should be recorded in metric notation (i.e., decimal fractions of centimeters) using a ruler or calipers.
- The same method of assessment and the same technique must be used to characterize each identified and reported lesion at baseline and during follow-up. For patients having only lesions measuring at least 1 cm to less than 2 cm must use CT imaging for both pre- and post-treatment tumor assessments.
- Imaging-based evaluation is preferred to evaluation by clinical examination when both methods have been used at the same evaluation to assess the antitumor effect of a treatment.

#### **11.32 Acceptable Modalities for Measurable Disease:**

**Conventional CT and MRI:** This guideline has defined measurability of lesions on CT scan based on the assumption that CT slice thickness is 5 mm or less. If CT scans have slice thickness greater than 5 mm, the minimum size for a measurable lesion should be twice the slice thickness.

- As with CT, if an MRI is performed, the technical specifications of the scanning sequences used should be optimized for the evaluation of the type and site of disease. The lesions should be measured on the same pulse sequence. Ideally, the same type of scanner should be used and the image acquisition protocol should be followed as closely as possible to prior scans. Body scans should be performed with breath-hold scanning techniques, if possible.
- PET-CT: If the site can document that the CT performed as part of a PET-CT is of identical diagnostic quality to a diagnostic CT (with IV and oral contrast), then the CT portion of the PET-CT can be used for RECIST and irRECIST measurements and can be used interchangeably with conventional CT in accurately measuring cancer lesions over time.
- Chest X-ray: Lesions on chest x-ray are acceptable as measurable lesions when they are clearly defined and surrounded by aerated lung. However, CT scans are preferable.
- Physical Examination: For superficial non-nodal lesions, physical examination is acceptable, but imaging is preferable, if both can be done. In the case of skin lesions, documentation by color photography, including a ruler to estimate the size of the lesion, is recommended.

